3.7 Identification of Second-Order Contacts

As discussed above, the rate of COVID-19 positivity in the second-order contacts of index cases (i.e. the contacts of first-order contacts) will be an endpoint used to assess the public health effectiveness of DCT for school populations. Several methods will be used to identify the second-order contacts of index cases:

• In-school secondary contacts: As part of their existing COVID-19 management policy schools are required to segment their population into distinct 'bubbles' (e.g., year group), membership of which is unique. Members of one bubble should not be interacting with members of another. As a result, all the contacts of a member of a specific bubble should also be members of the same bubble.

In the event of a positive index case within a bubble, the school will identify those bubble members it considers to be close contacts of the index case (this will often not be the entire bubble). These close contacts (i.e. 'first-order contacts' in the context of this study) are subject to self-isolation or DCT depending on their arm.

All other members of the index case's bubble will be considered second-order contacts for the purposes of this study. Membership of each bubble will be provided by participating schools at the start of the study, and should not vary during the study.

• Household contacts of first-order contacts: Another group of second-order contacts are individuals who live in the same household as a first-order contact. These may attend the same school or may not. These individuals will be 'identified' by querying routinely collected NHS Test and Trace testing data for individuals with the same residential address as any first-order contact. The method to identify household contacts will only identify household contacts who are in Test and Trace systems.

Within the scope of this study we do not intend (for operational reasons) to identify non-school, nonhousehold contacts of first-order contacts. As first-order contacts are required to maintain selfisolation outside the school environment (even if they are undertaking DCT) this group should be minimal in size. However, it is an acknowledged limitation of the study. We also do not intend (for similar reasons) to identify individuals within the school who are not a member of the same bubble as a first-order contact but have had close contact with them. We acknowledge this as another limitation of the study.

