Primary Attack Rate	The proportion of first-order contacts of the index case who themselves go on to be diagnosed with COVID-19
Secondary Attack Rate	The proportion of second-order contacts of the index case who themselves go on to be diagnosed with COVID-19

Figure 1: Definitions used for the chain of transmission

1. Rationale

When a person in a school / FE college¹ is diagnosed with COVID-19, first-order close contacts are required to self-isolate for 10 days. In schools, some groups of these close contacts (often managed as 'bubbles') may be quite large (e.g. a whole year group of over 250 pupils) and self-isolation has negative impacts on the education, psychological health and wellbeing of those affected². There is some evidence that suggests that compliance with self-isolation outside the school setting may be as low as 11% in asymptomatic contacts³ (although this may have improved since self-isolation has become a legal requirement). Modelling data shows daily testing of first-order contacts, using rapid lateral flow tests, could avert a similar level of onward virus transmission as self-isolation. In addition, recent work, has found that contacts identified by Test and Trace in the same household are more likely to become infected than first-order contacts at work, school or elsewhere. Primary age children are less likely to infect someone else and contact in schools with an infected child and are at a lower risk of transmission⁴.

It is proposed that when a positive case is detected, first-order close contacts will be offered the choice of being tested daily using rapid Lateral Flow Device antigen testing as an alternative to the requirement to self-isolate. A first-order contact with a negative test at the start of the school day can remain in school. However, they will be advised to self-isolate outside school. A person who tests positive with LFD will follow national protocols and self-isolate for ten days. This process is referred to here as Daily Contact Testing (DCT). DCT will enable the pupil's education to continue and reduced the health and wellbeing impacts of self-isolation.

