3.2 Methods

3.1 Overview of Design

This is a pragmatic cluster randomised controlled study. Eligible participating schools will be stratified according to institution type, size, Free School Meal prevalence and local COVID-19 prevalence and randomly allocated into the two study arms. A schematic summarising the study design and participant sub-groups can be found in Figure 2 below.

Regular Active Case Finding. In schools participating in either arm of the study, consent will be obtained from adults/parents/guardians for voluntary weekly testing of all students and biweekly testing of all staff⁵. Tests will be performed with lateral flow devices (LFD)*, and results will be reported in the NHS Test and Trace database. LFD Tests will initially be performed as an assisted test in a school setting. Once a reliable protocol for home testing and recording of LFD is available, schools will be offered the option for at-home self-testing for weekly case finding.

Individuals who test positive will self-isolate and identify first-order contacts according to national guidelines. In addition, symptomatic cases who test positive via NHS Test and Trace, and asymptomatic cases who test positive outside the in-school testing regimen will self-isolate and report their results to the school. All individuals with a positive test will be asked to provide a PCR swab test for genomic sequencing.

1. Intervention (Daily Contact Testing) Arm

a. Public Health Intervention: Consenting first-order contacts of a COVID-positive index case will receive daily contact testing for 7 days from the point of being notified they are a close contact⁶. This will consist of a daily LFD*. Those that receive a negative LFD result can attend school for that day, but other than travelling to and from school will be instructed to continue to self-isolate outside the school setting. Those that receive a positive LFD result should not attend school and will be instructed to self-isolate for 10 days according to national guidelines. The contacts of all first-order contacts (i.e. 'second-order contacts') will be identified to allow the determination of secondary attack rate.

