Routine qPCR of first-order contacts will be used to determine the performance of DCT testing with LFDs. Comparisons of PCR with the same day LFD will allow comparison between CT values and LFD results in a 'real world setting' These comparisons can also be used to compare the relative performance between assisted school-based testing and home/self-testing.

(iv) Number of COVID-19 cases transmitted to the first-order contacts of index cases ("primary attack rate").

The first-order close contacts of all index cases will be identified by the school based on their existing close contact management policy. LFD DCT testing and (for symptomatic individuals) routine NHS Test and Trace PCR testing will be used to calculate primary attack rate.

As above, genomic sequencing will be used, wherever possible, to exclude non-direct transmission events.

(v) Number of COVID-19 cases transmitted to the second-order contacts of index cases ("secondary attack rate").

The second-order contacts of all index cases will be identified (regardless of the COVID-19 status of the DCT-contacts) as described in Section 3.7. The COVID-19 status of these second-order contacts will be measured in two ways:

- i. Where the second-order contact is a consented participant in this study their COVID-19 status will be assessed by weekly LFD active case finding, and records kept by the school of any participants who become symptomatic and test positive via standard NHS Test and Trace community testing.
- ii. Where the second-order contact is not a consented participant in this study (e.g., household contact of first-order contact), analysis of routine NHS Test and Trace data will be used to determine if they subsequently become symptomatic and test positive in the community setting.

As above, genomic sequencing will be used, wherever possible, to exclude non-direct transmission events.

(vi) Number and proportion of school attendees testing COVID-19 positive in weekly active case finding.

LFD results and school attendance registers will be used to calculate active case finding rate. This will be compared between study arms, and to national schools' benchmark data collected via a survey of non-participating schools.

(vii) Proportion of student and staff who accept an offer of weekly active case finding testing with LFD devices.

Schools will maintain consenting records to allow participation rates to be calculated.

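### The household part of the secondary attack rate counts only people with a Test and Trace record, so it is inflated in both arms and could differ between arms through household members at the same trial school

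*Protocol*

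**What the plan says.** The Note on Definitions gives the secondary attack rate as "The proportion of second-order contacts of the index case who themselves go on to be diagnosed with COVID-19". Section 2.1, endpoint (v), asks for its number and rate among both school-based and household second-order contacts.

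The two groups are found in different ways (section 3.7):

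- **In school:** "All other members of the index case's bubble will be considered second-order contacts for the purposes of this study". Schools supply bubble membership at the start, so this denominator does not depend on testing.
- **Household:** members are found by "querying routinely collected NHS Test and Trace testing data for individuals with the same residential address as any first-order contact". The section adds that "The method to identify household contacts will only identify household contacts who are in Test and Trace systems", and says of these household members that "These may attend the same school or may not".

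For second-order contacts who are not consented participants, section 3.6 (v) takes the outcome from the same source: "analysis of routine NHS Test and Trace data will be used to determine if they subsequently become symptomatic and test positive". Consented participants are assessed by weekly LFD and by school records of symptomatic positives.

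Section 3.1 states that for weekly LFD testing in both arms "results will be reported in the NHS Test and Trace database". Section 3.9 expects 30% of children in control schools to consent to weekly testing. For the intervention arm the text gives 60% and Table 1 gives 40-60%.

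**The concern.** For household contacts, one database supplies both the list of people and, for non-participants, the outcome. A member who is diagnosed has a record because of the diagnosis. A member who is not infected has one only if tested for some reason. The result is a proportion among people with a record, not the proportion that the Note on Definitions describes, and it cannot be pooled with or set beside the bubble-based rate as if the two measured the same thing.

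If the chance that an uninfected member has a record also differed by arm, the two household rates would differ even with identical household spread. More routine testing under DCT would add negatives to the denominator and make DCT look better. Section 3.7 names this rate as an endpoint for judging the public health effectiveness of DCT, so the direction matters.

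**Working it through.** **1. Figures in the plan.** The protocol gives no expected household rate, so there is none to reproduce. The figure that rests on the uptake contrast is Table 2, which is not in dispute. For 15 self-isolating at 60% uptake, take two months, 2 control outbreaks of 51 people each and 4 intervention outbreaks of 15 + 3 = 18 people each (adding the index case and two DCT positives). A normal approximation gives (1.960 + 0.842)² × (2×51² + 4×18²) / (2×51 − 4×18)² = 7.85 × 6498 / 900, about 57 schools per arm against 58 in the table. The 30% v 60% contrast is therefore a working assumption of the plan.

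**2. Inflation in both arms.** Let *k* be the number diagnosed per 100 household members, all captured, and *f* the share of the other 100 − *k* who have a record. Then

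calculated rate = *k* / (*k* + *f*(100 − *k*)).

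The protocol gives neither *k* nor *f*, and sets no time window for records, so both are assumed. With *k* = 4:

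| *f* | Calculation | Calculated rate | Proportion diagnosed |
|---|---|---|---|
| 0.2 | 4 / (4 + 19.2) | 17.2% | 4% |
| 0.6 | 4 / (4 + 57.6) | 6.5% | 4% |
| 0.8 | 4 / (4 + 76.8) | 5.0% | 4% |

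The rate is too high whenever *f* is below 1. How much too high depends on a quantity the protocol does not supply.

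**3. Possible difference between arms.** Let *s* be the share of household members at the same trial school and *u* the uptake of weekly testing there. Assume that 20% of the other members have a record in both arms. Then *f* = *s*·*u* + (1 − *s*)·0.2. With *k* = 4 in each arm:

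| *s* | *f* control (*u* = 0.3) | *f* DCT | Control rate | DCT rate |
|---|---|---|---|---|
| 0 | 0.200 | 0.200 | 17.2% | 17.2% |
| 0.25 | 0.225 | 0.250 (*u* = 0.4) | 4/25.6 = 15.6% | 4/28.0 = 14.3% |
| 0.25 | 0.225 | 0.300 (*u* = 0.6) | 4/25.6 = 15.6% | 4/32.8 = 12.2% |

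At *s* = 0.25 the ratio of DCT to control is 25.6/28.0 = 0.91 at 40% uptake and 25.6/32.8 = 0.78 at 60%. At *s* = 0 it is 1.00.

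**4. Allowing weekly testing to find extra cases.** Step 3 holds the numerator fixed. As an alternative, assume a true household infection rate of 2% or 5% in both arms, a symptomatic test in 40% or 80% of infected members, 20% background records for members not at the school, and detection of infected same-school members by weekly testing in proportion to uptake (30% v 60%). With *s* = 0.25 the ratio is 0.78 to 0.84; with *s* = 0 it is 1.00. The extra cases narrow the gap but do not close it under these assumptions.

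**The case against.** Several points on the other side have weight.

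- **A reader might infer that the protocol expects the household denominator to differ by arm.** It does not say so. The 30% and 40-60% figures are children's consent to weekly testing in trial schools. Nothing predicts different testing of parents, younger siblings or pupils elsewhere. The only route supported by the text is household members at the same trial school, and their share is not given.
- **A reader might also infer that the rate would roughly halve under DCT.** Moving *f* from 20% to 40% for all household members gives 17.2% v 9.4% (4/23.2 and 4/42.4). With a 30-point uptake gap, that needs 0.20/0.30, about two-thirds, of household members to attend the trial school. With a 10-point gap it cannot occur by this route.
- **Nothing requires the record to predate the index case.** Without a time window, old records may count. *f* could then be high and the inflation small.
- **The restriction is disclosed, and the analysis may be a count.** Section 3.7 states the limit of the search. Endpoint (v) includes a number as well as a rate, and section 5.3 plans Poisson methods for secondary transmission. However, section 5.3 names no other denominator, and the disclosure does not discuss what the limit does to the rate. Section 3.7 labels two other gaps as limitations but not this one. An analysis plan could choose another denominator, but it cannot recover household members who were never listed.
- **The endpoint is secondary.** No sample size depends on it, and the in-school part is sound on this point.

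**Conclusion.** The household denominator in endpoint (v) does not match the protocol's own definition, and the resulting rate is too high in both arms. This follows from sections 3.6 (v) and 3.7 without further assumption, provided that some uninfected household members have no record. The size of the inflation is unknown: 5.0% to 17.2% against 4% in the illustration.

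Bias between arms is a possibility, not an established result. It would favour DCT, and its size depends on the share of household members at the trial school, the uptake actually achieved and the background record share. The 25% and 20% used above for the first and last of these are assumptions. The point merits a change to the text because this rate is meant to inform the judgement of DCT, but it does not touch the co-primary endpoints or the sample size.

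**What to change.** In sections 3.6 (v) and 3.7:

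- Do not use address matches as a denominator. Report newly diagnosed household members at the addresses of first-order contacts, per school-identified first-order contact, and state the period within which a diagnosis counts as new.
- Report this separately from the in-school rate, which keeps its bubble-list denominator.
- Base the between-arm household comparison on symptomatic community diagnoses, the source that section 3.6 (v) already names for non-participants. Report LFD-detected household cases descriptively alongside, so that they are not lost.

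With an average of *h* other household members per first-order contact and 4 diagnosed per 100, the measure is 0.04*h* in each arm whatever the value of *f*. The dependence on who happens to have been tested without being infected is removed.

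The cost is wording and a different denominator; the address query stays the same. The result is a count per first-order contact, not a true attack rate. It is not adjusted for household size, and it relies on schools naming first-order contacts in a similar way in both arms.

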3.8 Assessment of Behavioural and Other Outcomes

Assessment of the behavioural components of the evaluation framework will include the following:

- 1. Survey of a) self-reported out of school activities and contacts (for comparison in testnegative, test-positive and self-isolating participants); b) views of testing (compared with selfisolation)
- 2. PPI input and qualitative research to understand views and experiences of and responses to testing of pupils, parents and school staff teachers and others

Participants in both the Interventional and Control Arms will be invited to complete a very brief online survey; this will include all participants who are a first-order contact of a positive index case. Measurement will be on day 7 after notification of being the contact⁷, using self-report measures of social contacts and other behaviours adapted from measures already in use. To promote honest self-reporting, an anonymous survey instrument will be used (as in the previous 'Agile Lighthouse' evaluation of DCT), which can be found in Appendix 2.

Outcome 2 focuses on gathering the perceptions, experiences and beliefs of those involved in the testing process, including pupils, parents, teachers and administrators. In collecting this data, it is crucial that the burden on teachers and school staff is reduced as far as possible during what is already an extremely challenging time for them. We have explored the potential for using existing research vehicles (e.g. the Pupil and Parent Panel omnibus survey), but these would not allow us to deliver the objectives of the present study. The bespoke data collections have therefore been streamlined to lower burden. The approaches that will be used are:

- User research carried out in two waves within both Phase 1 and Phase 2:
 - Wave 1: At the beginning of the testing period to explore the practicalities of delivering the protocol within the 'intervention arm' schools. This will be no more than ten interviews (anticipated approx. 20-30 minutes, no more than 1 participant per school site) with school staff (teachers and non-teachers) involved in management/implementation focusing on the process and expectations for the testing. Data will enable a view of the study implementation (allowing adjustments to be made if required) as well as the feasibility of wider rollout.
 - Wave 2: Follow-up interviews (anticipated approx. 20 minutes) with these participants towards the end of the study period to collect their reflections having experienced more of the testing, again focusing on the process and feasibility of wider roll-out.
- Interviews with pupils, parents and staff in a sample of the schools involved in the testing (both Interventional and Control arms), looking to understand in more depth experiences of the testing process, beliefs about testing, perceptions of positive and negative test results and potential improvements and issues affecting take-up and impact on behaviour. Participants will be invited to take part in recorded online or telephone interviews (20 to 30 minutes)

⁷ For clarity, the day on which they are notified they are a contact is Day 0

outside of school opening hours, and will receive an online voucher as reimbursement for their time. The sample will include staff, parents and pupils from different schools, with different ages, ethnic and socioeconomic backgrounds, and with positive and negative test results. Recordings will be fully transcribed, anonymised and analysed for emerging themes.

Parent/Guardian consent for pupils' participation in social research will be obtained via schools prior to commencement of fieldwork. More detail on social research design is included in Appendix 7.

3.9 Sample Size

Advice on the appropriate sample size for this study has been sought from [name] at the University of Oxford.

The challenge with setting a non-inferiority margin for transmission events is that the meaning of a non-inferiority margin is highly dependent on the control group event rate. For example, if the control group event rate is 20%, then, depending on the other advantages of the intervention, it may be reasonable to set a non-inferiority margin of 10%, i.e., to exclude increases of more than 10% absolute or 50% relative. But if the control group event rate is 1%, a 10% non-inferiority margin is very unlikely to be considered reasonable. However, choosing the wrong control rate can have enormous consequences for the power of a trial to determine non-inferiority within a pre-defined bound⁸.

At present, it is extremely difficult to get any estimate of a control group event rate for transmission over the next 3 months, and hence it is impossible to pre-define what might be a meaningful non-inferiority margin, given the hypothesised benefits of the intervention. We therefore power the trial to determine superiority of the intervention on school attendance; if superiority is demonstrated on the primary endpoint, we will ask an independent committee to judge whether the 95% CI for the difference between intervention and control schools on transmission events is sufficiently close to no difference such that the benefits outweigh any potential risks.

The primary endpoint of the study is the number of missed days at school compared to the control group. The following scenarios will illustrate the effect of the intervention on school attendance

The number of Covid-19-associated missed days at school is dependent on the number of positive cases identified and the number of contacts of these cases that are self-isolating. Each positive case is self-isolated for 10 days. In the control group all first order contacts will also be self-isolated for 10 days. It is expected that this trial will occur in the summer term when the number of cases in a school will be low. For instance, it is expected that in the control group about 30% of children (and their parents) will consent to participate in regular weekly active case finding testing. For the purposes of the power calculation, it is assumed that the expected number of index cases identified is about 1 outbreak/month. Each index cases will lead to identification of 50 children in their bubble who will need to self-isolate each for 10 days. The number of index cases identified is a Poisson distribution with mean 1/month with each index cases leading to 510 missed school days.

In the intervention group, it is expected that a more complex set of interactions will occur. The ability to avoid self-isolation by DCT is likely to make participation in weekly active case finding testing more

⁸ Quartagrio et al, 'Handling an uncertain control group event risk in non-inferiority trials: non-inferiority frontiers and the power-stabilising transformation' (2020)

attractive with an increase in consent to voluntary weekly active case finding testing to 60%. This in turn will lead to the identification of more positive cases with initially an expected number of 2 different index cases identified per week. However, it is expected that 70% of children will volunteer for DCT and therefore only 15 children (25% of 50) will self-isolate. In addition, about 2 contacts will be identified by LFD testing as positive during DCT (5% of 35). It is expected that these 2 children will only have contacts within the bubble and therefore they will not lead to identification of more children. In all, each index cases will lead to the index cases or 360 missed schools / month

In addition, the intervention will lead, over time, to a decrease in transmission and therefore detection of cases through an increased identification and isolation of true positives, itself arising from an increase of uptake of weekly active case finding testing. However, this decrease will be offset by the possible increase in in-school transmission by infectious children not undertaking DCT who attend school.

It is expected that the trial will start in the Summer term with 100 schools enrolled into each arm. However, it is likely that only 50% of enrolled schools will manage to sustain the trial leaving only 50 schools in each group.

	Control Group	Intervention Group
Number of schools successfully participating	50	50
Proportion of children consenting to mass testing	30%	40-60%
Initial number of outbreaks detected/school	1/month	2/month
Number self-isolating (incl. index case and) each for 10 days	51	10-30
Number of schools in each arm	50	50

*Including index case and 2 cases in each DCT bubble of 50 children test positive and therefore need 10 days of self-isolation

Table 1: Assumptions in Power calculation

The number of schools required in each arm to determine whether school attendance has been increased by the intervention will depend on the number of children volunteering for DCT and the increase in the proportion of children consenting for weekly active case finding testing.

Assuming that 30% of the control arm participate in weekly active case finding testing, the number of schools per arm for a two month study is shown in the following table (power of 80%, two-sided alpha (0.05))

Number (per index case) in intervention group	Proportion if children consenting to weekly active case finding testing in intervention arm		
self-isolating and not undertaking DCT	40%	50%	60%
7	10	12	14
8	11	13	15

911141810121521111317241214192913152236141826451518305816203579172343112182653170192967172033871172138117				
11 13 17 24 12 14 19 29 13 15 22 36 14 18 26 45 15 18 30 58 16 20 35 79 17 23 43 112 18 26 53 170 19 29 67	9	11	14	18
12 14 19 29 13 15 22 36 14 18 26 45 15 18 30 58 16 20 35 79 17 23 43 112 18 26 53 170 19 29 67 17 20 33 87 112 21 38 117 117	10	12	15	21
13 15 22 36 14 18 26 45 15 18 30 58 16 20 35 79 17 23 43 112 18 26 53 170 19 29 67 1 20 33 87 1 21 38 117 17	11	13	17	24
14 18 26 45 15 18 30 58 16 20 35 79 17 23 43 112 18 26 53 170 19 29 67	12	14	19	29
15 18 30 58 16 20 35 79 17 23 43 112 18 26 53 170 19 29 67	13	15	22	36
16 20 35 79 17 23 43 112 18 26 53 170 19 29 67	14	18	26	45
17 23 43 112 18 26 53 170 19 29 67 20 33 87 21 38 117	15	18	30	58
18 26 53 170 19 29 67 20 33 87 21 38 117	16	20	35	79
19 29 67 20 33 87 21 38 117	17	23	43	112
20 33 87 21 38 117	18	26	53	170
21 38 117	19	29	67	
	20	33	87	
22 45 166	21	38	117	
	22	45	166	
23 53	23	53		
24 64	24	64		
25 78	25	78		
26 98	26	98		
27 125	27	125		

Table 2: Relationship between number of schools required per arm and study participation rates

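### Section 3.9 gives contradictory sample-size inputs, and 50 schools per arm give about 74%, not 80%, power in its one worked scenario

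*Protocol*

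**What the plan says.** All of this is in Protocol section 3.9 unless noted.

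- **Target.** Table 2 is built for "power of 80%, two-sided alpha (0.05", and "the number of schools per arm for a two month study is shown in the following table".
- **Control arm.** Index cases are Poisson with mean 1 per school per month. Each sends 51 people (the case and 50 contacts) home for 10 days, which is 510 missed days.
- **Intervention arm, worked scenario.** Consent to weekly testing rises from 30% to 60%, with "initially an expected number of 2 different index cases identified per week". With 70% uptake of daily contact testing (DCT), "only 15 children (25% of 50) will self-isolate". About 2 contacts are then found positive in DCT. The result is stated as "each index cases will lead to the index cases or 360 missed schools / month".
- **Table 1.** Outbreaks detected per school are 1 per month in control and 2 per month in intervention.
- **Schools.** 100 are enrolled per arm, but "it is likely that only 50% of enrolled schools will manage to sustain the trial leaving only 50 schools in each group".
- **Table 2.** The rows for 14 and 15 isolating contacts, run together in the extracted text, read "14 18 26 45 15 18 30 58". For 15 isolating, the need is 18, 30 or 58 schools per arm at 40%, 50% or 60% consent.
- **Variation between schools.** Section 3.9 states no CV, intracluster correlation or overdispersion term. Section 1 says that groups of close contacts "may be quite large (e.g. a whole year group of over 250 pupils"), and section 3.1 stratifies randomisation on size and local prevalence, among other factors.

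**The concern.** Attendance is the only endpoint for which the trial is powered. Section 3.9 also asks the independent committee to judge the transmission interval only if superiority on attendance is shown. An optimistic power figure therefore bears on both decisions.

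The section invites that optimism in three ways. The text and Table 1 disagree on the intervention outbreak rate, and a reader who takes the text at its word gets an effect in the wrong direction. The number of schools expected to remain falls short of what Table 2 asks for in the only scenario the text works through. And the table appears to treat every school as having the same outbreak rate and every index case as having exactly 50 contacts.

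**Working it through.** **1. Which inputs agree**

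- *Outbreak rate.* 2 per month × (15 isolating + 2 DCT positives + 1 index case) × 10 days = 2 × 18 × 10 = 360 days per month. This matches the protocol's figure and Table 1. At 2 per week the total would be 2 × 4 × 180 = 1,440 (four-week month) or 2 × 52/12 × 180 = 1,560 days per month, against 510 in control.
- *Isolating contacts.* 70% uptake leaves 30%, and 30% of 50 = 15. 25% of 50 would be 12.5. The 360 days needs 15.

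**2. Reproducing Table 2**

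The protocol does not print its formula, so the method below is inferred from the fit. In units of 10 days, over 2 months, per school:

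- mean = λs and variance = λs², a Poisson number λ of outbreaks each of fixed size s;
- control: λ = 2, s = 51, so mean 102 and variance 2 × 51² = 5,202;
- intervention: λ = 2 × (consent / 30%), s = row value + 3;
- worked scenario: λ = 4, s = 18, so mean 72 and variance 4 × 18² = 1,296.

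Normal approximation: n = (1.960 + 0.842)² × (5,202 + 1,296) / (102 − 72)² = 7.849 × 6,498 / 900 = 56.7, or 57. A Welch t-test using the noncentral t distribution gives **58**, the printed value. The same method matches 48 of the 49 printed cells exactly. The exception is 14 isolating at 40% consent, printed 18 and computed 17.

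**3. Power at 50 schools per arm, worked scenario**

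Standard error = √(6,498 / 50) = 11.40, and 30 / 11.40 = 2.63. Welch t power is **73.8%**. The normal approximation gives 74.9%, and a simulation of 20,000 trials gave 75.0%.

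**4. What 50 schools cover in Table 2**

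| Consent | Printed cells | Cells needing ≤ 50 | Largest row covered |
|---|---|---|---|
| 40% | 21 | 16 | 22 isolating |
| 50% | 16 | 11 | 17 isolating |
| 60% | 12 | 8 | 14 isolating |
| Total | 49 | 35 | |

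At 60% consent the limit is 14 isolating (45 schools needed, 84% power at 50), one fewer than the 15 that the text expects.

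**5. Adding variation beyond Poisson**

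The protocol gives no value, so every CV here is an assumption. The variance per arm becomes λs²(1 + CVc²) + (λs·CVr)², where CVc is for contact-group size and CVr for the between-school rate.

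| CVr | CVc | Variances (control, intervention) | Power at 50 | Needed per arm |
|---|---|---|---|---|
| 0 | 0 | 5,202; 1,296 | 74% | 58 |
| 0.25 | 0 | 5,852; 1,620 | 68% | 67 |
| 0.5 | 0 | 7,803; 2,592 | 54% | 92 |
| 0 | 0.5 | 6,502.5; 1,620 | 64% | 73 |

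**6. If all 100 enrolled schools per arm contribute data**

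Worked-scenario power is 96% if DCT is sustained and no variation is added, and 83% at CVr = 0.5. If half the intervention schools revert to control practice and all are analysed as randomised, the intervention mean is (102 + 72)/2 = 87. Its variance is (5,202 + 1,296)/2 + 15² = 3,474, and power is about 36%.

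**The case against.** The protocol presents scenarios, not a single design point. Table 1 gives ranges (40–60% consent, 10–30 isolating), the text says that the number of schools depends on uptake, and Table 2 openly prints 58, 79, 112 and 170. A reader might infer that the protocol claims 80% power with 50 schools in the worked scenario. It makes no such claim, and that scenario sits in the least favourable consent column. This stands, and it limits the shortfall to about 6 percentage points in one disclosed scenario. It remains the only scenario that the text works through, and nowhere does the section say which cells 50 schools cover.

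A reader might also infer that between-school variation is ignored altogether. It is not: Poisson variation between schools drives Table 2, and section 5.3 plans a per-school analysis, so clustering within schools is respected. Only variation beyond Poisson is absent.

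Nor did the per-week rate enter the calculation. Table 2 uses 2 per month at 60% consent, so the 1,440 to 1,560 days show what the text implies, not a flaw in the table.

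The size of any extra variation is unknown. Stratifying on size and prevalence, and expressing absence as a proportion of pupils, could remove some of it. The figure of over 250 describes a whole year group, and section 3.7 says that close contacts are often fewer than the full bubble. So the figures in step 5 are illustrations. These points do not justify setting the extra variation to exactly zero.

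Finally, it would be too strong to say that a miss on attendance leaves transmission unanswered. Transmission is a co-primary endpoint and will be estimated in any case. Only the committee's judgement is conditional.

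**Conclusion.** The point holds. Two inputs in section 3.9 are wrong as written: the weekly rate contradicts Table 1, the 360 days and Table 2, and 25% contradicts the 70% uptake and the 15 children. In the worked scenario, 50 schools per arm give about 74% power against the stated 80%, for which Table 2 requires 58. This follows from the protocol's own numbers and a method that matches 48 of 49 printed cells.

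The table also assumes no variation beyond Poisson chance in outbreak rate or group size, although the protocol itself describes differences in both group size and local prevalence. How far that lowers power cannot be derived from the document. The 68% (rate CV 0.25 alone) and 64% (group-size CV 0.5 alone) hold only under those assumed values. The shortfall also depends on the protocol's expectation that half the schools drop out.

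**What to change.** 1. In the section 3.9 text, change the intervention index-case rate from per week to per month, and 25% to 30%.
2. State that 50 schools per arm give about 74% power in the worked scenario, or state that 80% at 60% consent holds only if at most 14 contacts isolate.
3. Recompute Table 2 over a stated range of contact-group and between-school rate CVs, labelled as assumptions.
4. If register attendance is also kept for all 200 randomised schools and analysed as randomised, state power for that analysis separately. The 74% does not describe it: power is about 96% at 100 per arm if DCT is sustained and no variation is added, and about 36% if half the intervention schools revert to control practice.

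The cost is two text corrections and a recalculation. No schools are added, so the change discloses the shortfall without removing it, and the stated power becomes less favourable.
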